Evaluation Goal:

To evaluate the safety and acceptability of the ShangRing device for nonsurgical circumcision in routine clinical settings, as a part of a comprehensive HIV prevention program for males in VMMC programs.

Evaluation Endpoints:

Primary Endpoint: the proportion of males experiencing mild, moderate and severe adverse events (AEs) associated with ShangRing circumcision procedures, including both intra- and post-operative events, and all device-related malfunctions (e.g., early spontaneous detachment).

Secondary Endpoints:

- Training needed for proficiency using the ShangRing device, including number of procedures to become fully proficient at applying and removing the ShangRing device.
- Client and provider acceptability, client satisfaction, and duration of procedure.
- The percentage of clients clinically healed 49-52 days post-placement of the ShangRing device, and the time at which point all clients are clinically healed.

Evaluation Design

Training Phase: this phase will be used to evaluate the training requirements for implementation by mid-level providers, to preliminarily assess acceptability to providers, and to monitor logistical needs. Each clinician will perform no fewer than 10 ShangRing device placements, and 5 ShangRing removals before start of the next phase (implementation pilot).

Implementation Pilot: following the training period, 575 male clients will be recruited to undergo circumcision with the ShangRing device in the context of routine service delivery.

Data will be collected at up to at least 5 points in time: at enrollment and device placement (day 0), at device removal (day 7), during a follow-up phone call (day 10), in-depth qualitative interviews for 50 purposefully selected clients (day 28), at an in-person follow-up visit to assess wound healing (day 49), and at subsequent weekly visits to assess healing for those not completely healed at day 49.

Upon completion of the implementation pilot, the data will be analyzed and used to assist with policy decisions and recommendations on ShangRing use in adult male circumcision programs.

Section C: Protocol

Introduction

Voluntary Male Medical Circumcision (VMMC), VMMC Devices and ShangRing

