To evaluate the safety and acceptability of the ShangRing for device-based circumcision in routine clinical settings, as a part of a comprehensive HIV prevention program for males aged 13 and older in Tanzania.

Evaluation Objectives

The specific objectives of the proposed implementation pilot is to:

- Describe/assess the safety of the ShangRing device by the occurrence of clinical adverse events (calculated as a rate), when circumcision is performed by trained mid-level providers;
- Ascertain capacity and required clinical capabilities of clinical staff of various cadres to carry out ShangRing procedures;
- Describe/assess male client and provider acceptability of the ShangRing device and process (e.g. need to return to the clinic for device removal, tolerance for leaving device in situ);
- Assess the percentage of clients clinically healed 6 weeks (42 days) following the removal of the device;
- Determine the time at which point all clients are physically healed following the removal of the device.

Primary Endpoint

The primary endpoint related to the goal and objectives of the evaluation is to:

- Measure the incidence of mild, moderate and severe AEs associated with ShangRing procedures including both procedure and post-procedure events, and all device-related malfunctions such as early spontaneous displacement. The primary endpoint will be assessed at device placement, at device removal, 3-days post removal, at the day 49 post-placement healing assessment, and at any unscheduled visit in that time frame. Adverse events will be measured and described in the following ways:
 - Total numbers and types of known AEs occurring among clients, including all severities of AEs (mild, moderate, severe) and serious AEs (see below), including detailed information about all instances of device displacement/detachment/self-removal/malfunction, need for medical attention or intervention, and final outcomes in those experiencing AEs.
 - Total number of clients with known AEs (may be different from above if clients experience multiple AEs), including all severities of AEs and serious AEs.

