 - Total number of clients who fail to return to the circumcision site (or site indicated by service providers) for recommended follow-up (whether removal visit or AE follow-up).
 - Proportion of all men receiving VMMC services at the evaluation sites who choose ShangRing method instead of surgical circumcision.
- Document provider acceptability of ShangRing, to be measured by the following:
 - Provider perceived ease of application, ease of removal, ease of clinical management of adverse events, and preferences in comparison to conventional circumcision methods.
- Document duration of procedures, and problems encountered during procedures and post-procedure care, to be measured by the following:
 - ShangRing application time will be measured, including the overall time the client is on the procedure table, and the time required for discreet application activities: client preparation time (including application of local anesthetic and sizing), marking and device application, and clean-up time.
 - ShangRing removal time will be measured, including the overall time the client is on the procedure table, the time required for discreet removal activities, and time for post removal instructions given to the client.
- The percentage of clients determined by a clinician to be clinically healed 49-52 days post-placement of the ShangRing device (42 days post-removal), and the time at which point all clients are clinically healed.
 - Healing will be documented by evaluation staff, who will take photographs of the client's genital area during the follow-up visits.
 - Healing will meet the definition of clinical healing after VMMC, defined as:
 - "Intact epithelium (unbroken skin) covering the wound as judged by the provider on visual inspection, meaning that none of the following are present: sutures, scabbing, drainage, moisture, gaps between epithelial edges or ulceration."²⁵

Evaluation Design

Overall Design

This implementation pilot is comprised of two phases: a training phase and the main implementation pilot. During the training phase clinicians at the participating sites will be trained in the use of the ShangRing device. Upon completion of the training phase, the main implementation pilot will begin. The implementation pilot is a single arm, open label, prospective cohort evaluation.

Description of Evaluation Populations and Catchment Areas

Shinyanga, Tanzania

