Males who present with exclusion criteria for one of the medical reasons listed above will be referred to the appropriate specialist for management of their conditions. Additionally, any men who have an anatomic contraindication but still want circumcision, can be referred to an urologist for further management. In keeping with standard national practice, clients presenting with specific disease conditions such as STIs or TB may be treated on-site or referred for care elsewhere if appropriate services are not available on site. Furthermore, males who are HIV+ will be assessed to determine if they are on antiretroviral therapy (ART). Those not on ART will be referred for ART.

Client Withdrawal Criteria

A client has the right to withdraw from the evaluation at any time, for any reason, without prejudice to his future medical care by the provider or the health facility (see Appendices V and VI for the client and minor client assent forms). If a client withdraws after consent, but prior to device placement, the client will be replaced until the desired sample size is reached and the data will be excluded from analysis. If a client withdraws after device placement, the client will not be replaced and the existing data will be included in the analysis, but no attempts will be made to collect further data other than that required for clinical documentation of the removal visit. The reason, timing and circumstances of the withdrawal will be documented and analyzed. The client will subsequently not be included among those selected for the day 28 in-person interview, nor will they be asked to return for the day 49 follow-up visit to assess healing. When the client withdraws, they will be informed that they may still return to the clinic for removal of the device as scheduled, and contact the clinic should they have further questions, suffer an AE, or experience other difficulties healing.

A client will be informed in advance that if he wishes to withdraw from the evaluation after ShangRing placement but before scheduled removal, he must still return to the provider for device removal on day 7 for his own health. The client will also be advised that once applied, it is not safe to remove the device before day 5. If the client requests removal on day 5 or 6, it will be removed as requested. The number and reasons for client withdrawals will be recorded and included in the final evaluation report (See Appendix XXII).

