Procedure for Handling Clients Lost-to-Follow-Up

Clients who are lost to follow-up after device placement, and therefore do not return to have the device removed, will not be recorded as experiencing an AE, and also will not be included in calculations when measuring AEs.

In the event that a client refuses to return for follow-up, ShangRing has been shown to detach on its own. Studies show that for those clients who do not come in to have the device removed, and wear it for more than

seven days, the ShangRing will eventually spontaneously detach on its own, and healing will progress normally. In one study, complete detachment of the device occurred in 66.7% of men who wore the device for more than seven days, and 14% of men requested removal of a partially detached device 8-14 days after placement. No severe or serious AEs were reported among this group.²⁹

A study of delayed removal of ShangRing in Kenya found that in 81.8% of men the ShangRing had completely detached on its own between 10-16 days after circumcision.³⁰ By 21 days following the circumcision the ring had at least partially detached in 100% of men, and was completely detached in 93.7%. While the ShangRing has been found to be safe if left on, this is not the recommended standard of care for the purposes of this evaluation, and clients will be followed up with for device removal as described in this protocol.

Provider Participant Inclusion Criteria

Providers meeting the following criteria will be included in the evaluation:

- Adult aged 18 or older
- Employed as a medical doctor, Assistant Medical Officer, Clinical Officer, professional nurse, or enrolled nurse at the participating sites in Shinyanga, Tanzania
- Experienced in providing conventional surgical circumcision
- Trained and certified in ShangRing circumcision techniques for the current evaluation by a trainer who is trained in ShangRing application, and has performed a minimum of 10 placements and 5 removals. The evaluation team will bring in ShangRing master trainers from countries with prior ShangRing experience (i.e. Kenya, Zambia) to train providers based in Shinyanga who will then train mid-level providers to conduct ShangRing circumcision, or send physicians from Tanzania to these countries for training.
 - Trained and competent in identifying and managing complications related to ShangRing circumcision.
 - Trained and competent in screening clients to determine their eligibility for ShangRing circumcision.

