Sites should provide a brief orientation to other health centers in the catchment area. The purpose of this orientation is to provide these health centers with an overview of the pilot, to offer the health centers guidance on how to provide care for any pilot clients that may present to their clinic, and to request the health centers alert the pilot sites in the event that a client from the pilot seeks follow-up care from the center (i.e. in the case of the AE), and provide the health centers with contact information for implementation pilot staff in order to do so.

Sample Size, Data Collection and Analysis Timeline

The total sample size for this implementation pilot is 575 male clients at the selected sites in Shinyanga, Tanzania. Both HIV- and HIV+ men will be included in the sample. The sample size of 575 males is consistent with the framework for circumcision device introduction as proposed by the WHO (see appendix I below). Additionally, this sample size is powered to detect the occurrence of adverse events, which is estimated to be 2%. A minimum of 335 males are necessary for 95% confidence that the population proportion is within $\pm 1.5\%$ with an observed adverse event rate of 2%. An additional 240 males will be recruited for further confidence in the results, and to align with the WHO framework. The evaluation teams will enroll males until the 575 sample size figure is achieved. All 575 males to be considered for the data analysis will be enrolled upon completion of the training phase.

All data collection will begin as soon as the first circumcision of an enrolled client occurs. Data will continue to be collected until the country has performed 575 circumcisions with the ShangRing device, and all post-circumcision follow-up data collected from clients as detailed in this protocol is complete. After the 575 circumcisions and all follow-up information is collected, the analysis of data as described per the primary and secondary endpoints will begin. If after the country has finished 575 circumcisions, and wishes to conduct the analysis necessary to inform national policy for the purposes of implementing the ShangRing device on a wider scale, that country may continue to enroll clients, and the first 1000 circumcisions performed should be monitored through active surveillance, as detailed in the WHO framework, and the country should perform its own data analysis as needed.³¹

Supplies and Logistics

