Follow-Up Visits

Active follow-up will be initiated for clients who fail to return on day 7 post-placement to have the device removed, or for other visits (e.g. AE follow-up) recommended by the ShangRing clinician. Each implementing site will assign staff to conduct follow-up telephone calls and home visits as needed. All active follow-up efforts will be documented on the appropriate forms designed for this purpose (Appendix XI). For clients who fail to return for device removal on day 7, active follow-up will start on day 8. Active follow-up will start with telephone calls to the contact number(s) provided by client and recorded on the locator information sheet at enrolment. An

introductory script for contacting clients by phone is attached as Appendix X. If a client is not reachable through direct voice calls, short text message reminders will be sent to his contact phone number. The reminder text message will include client name and specify the name and phone number of the clinic reaching out to him. The text message will not include the purpose of appointment visit for which the reminder is sent. Up to five calls will be made to reach the client; one per day starting on day 8, and continuing over the next 4 days through Day 12 (5 days post-procedure).

Once contact is made, the staff member will reinforce the importance of device removal and encourage the client to return to the circumcision site. If the client states that he is not able to return by day 9 post-placement, or the schedule day, or does not in fact return by day 9 or the schedule day, the staff member will attempt to verify the addresses provided to schedule an appointment at one of the address locations provided for device removal on day 9, or as soon as possible. If the client has not been successfully contacted by day 9 or the scheduled day, home tracing visits to the address he provided will begin. These will total up to 4 visit attempts on different days if necessary to reach the client.

For clients not under follow-up for AEs who miss scheduled visits other than the day 7 visit, follow-up will be done through phone by text messages or voice calls only, except in exceptional circumstances where a clinician deems physical follow-up necessary.

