The staff member will discuss the clinical course and AE with the client and encourage the client to return for review to the health facility where the circumcision procedure was performed, if deemed medically necessary. If the client does not return for follow-up visits deemed medically indicated, active tracing will be initiated. In situations where clients cannot be reached by telephone or located through physical tracing, after a total of 8 calls and 4 visits on different days, the case will be directed to the attention of the site manager for disposition. In this case, these clients will be considered to have experienced a moderate AE by default, unless follow-up indicating otherwise is able to be completed.

In-Person Qualitative Interviews

The evaluation staff will select 50 individuals to participate in a more in-depth in-person qualitative interview to be held 28 days post-circumcision. Fifty clients were chosen as the sample size, based on prior experience with evaluating acceptability of circumcision devices, which suggests that 50 is sufficient to obtain the necessary range of views and opinions. Only males aged 18 years or older will be eligible to be selected to participate in the qualitative interviews. All clients will be asked when they are enrolled if they are willing to participate in an interview. The first 50 clients, aged 18 years or older, to indicate willingness at enrollment to participate will be asked to interview. If after contacting these men for an interview, not all are able to participate, clinic staff will

continue to proceed down the list of clients in the order in which they enrolled and agreed to an interview, until 50 clients are selected. These interviews will be used to assess client pain, discomfort, and satisfaction with the procedure. Males selected for the qualitative interviews may refuse to participate or withdraw at any time, the reason for their refusal/withdrawal will be recorded and reported. Clients will be offered a small amount to reimburse their travel and time spent for the interview (estimated to be between 20-25 USD/45,000-56,500 Tanzanian Shillings but not to exceed 30 USD/67,900 Tanzanian Shillings).

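### The loss-to-follow-up rule removes clients from the AE rate even when an AE is already known, and contradicts the default-AE rule for untraced callers

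*Protocol*

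**What the plan says.** Under Procedure for Handling Clients Lost-to-Follow-Up, clients lost after placement who do not come back for removal "will not be recorded as experiencing an AE, and also will not be included in calculations when measuring AEs".

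Other sections bear on the same clients:

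- **Evaluation Endpoints (Executive Summary).** The primary endpoint is defined as "including both intra- and post-operative events, and all device-related malfunctions (e.g., early spontaneous detachment".
- **Primary Endpoint (Evaluation Design and Methods).** Assessment starts at device placement and covers unscheduled visits. One required summary is "Total number of clients with known AEs (may be different from above if clients experience multiple AEs". The day 0 form (Appendix IX) asks whether an AE occurred during placement.
- **Telephone Calls Initiated By Clients due to AEs.** If a caller does not return when a visit is medically indicated, and cannot be reached after 8 calls and 4 visits, "these clients will be considered to have experienced a moderate AE by default, unless follow-up indicating otherwise is able to be completed".
- **Client Withdrawal Criteria.** For a client who withdraws after placement, "the client will not be replaced and the existing data will be included in the analysis".
- **Follow-Up Visits.** A missed removal visit triggers up to five calls, text messages and home tracing: "These will total up to 4 visit attempts on different days if necessary to reach the client".
- **Minimum Site Requirements.** Sites are to "request the health centers alert the pilot sites in the event that a client from the pilot seeks follow-up care from the center".
- **Secondary Endpoints.** The protocol will report the "Total number of clients who fail to return to the circumcision site".

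**The concern.** The rule contains two instructions. The first, that loss is not itself scored as an AE, is reasonable. The second takes the client out of the AE calculation altogether, whatever is already known about him. A harm observed on day 0 can therefore leave the primary safety rate because of what the client did later.

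The rule also meets the default-AE rule head on for one group: clients who phone about an AE while wearing the ring and are then never found. Two analysts, each following the protocol, would classify the same man in opposite ways. The rate is meant to inform national policy on the device, so it should not depend on which paragraph the analyst read.

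**Working it through.** **1. The same client under each section**

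| Client | Loss-to-follow-up section | Other section |
|---|---|---|
| AE recorded at placement, never returns, not traced | Not an AE, excluded | Primary Endpoint: a client with a known AE, counted |
| Phones about an AE before removal, not traced | Not an AE, excluded | Client-initiated calls: moderate AE by default |
| AE recorded at placement, then withdraws | Not applicable | Withdrawal Criteria: existing data kept |

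The first two rows are conflicts. The third is an inconsistency of principle only, since withdrawal and loss are different dispositions. The second row is a real possibility: the call rule is not limited to calls after removal, and placement counselling invites clients to phone at any time.

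**2. The plan's own figure**

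Inputs from Sample Size, Data Collection and Analysis Timeline: AE rate 2%, half-width 1.5 points, 95% confidence.

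n = 1.96² × 0.02 × 0.98 / 0.015² = 334.6, rounded up to 335. This reproduces. At n = 575 the half-width is 1.96 × √(0.02 × 0.98 / 575) = 1.14 points. The finding does not depend on the sample size.

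**3. Sensitivity of the rate**

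Assumptions, because the protocol gives no loss rate: 575 placed; 1%, 2% or 5% lost before removal (6, 12 or 29); 11 AE clients among those who return, about 2%. Upper limits are exact (Clopper-Pearson), two-sided 95%.

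| Lost | Rate under the rule (upper limit) | All placed, no lost client had an AE | All placed, every lost client had an AE |
|---|---|---|---|
| 6 | 11/569 = 1.93% (3.43%) | 11/575 = 1.91% | 17/575 = 2.96% |
| 12 | 11/563 = 1.95% (3.47%) | 11/575 = 1.91% | 23/575 = 4.00% |
| 29 | 11/546 = 2.01% (3.58%) | 11/575 = 1.91% | 40/575 = 6.96% |

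The second column stays the same however many of the lost had an AE on record.

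**4. Effect of AEs already known**

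One AE client is 1/575 = 0.17 points, or 1/11 = 9% of the expected number. Restoring known AEs over all 575:

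- 1 known: 12/575 = 2.09% (upper limit 3.62%)
- 3 known: 14/575 = 2.43% (4.05%)
- 6 known: 17/575 = 2.96% (4.69%)

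**5. Scale against planned precision**

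The gap between the all-AE bound and the reported rate is:

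- 7 lost: 18/575 − 11/568 = 3.13% − 1.94% = 1.19 points, above the 1.14 that applies at n = 575
- 8 lost: 19/575 − 11/567 = 3.30% − 1.94% = 1.36 points
- 9 lost: 20/575 − 11/566 = 3.48% − 1.94% = 1.53 points, above the 1.5 the plan ties to n = 335

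A missing-data bound and a sampling half-width are different quantities, so this gives scale only.

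**The case against.** **The rule may only mean that non-return is not presumed to be an AE.** The text after it, on rings that detach unaided, supports that reading of the first instruction. It does not cover the second, which excludes the client from the calculation.

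**Known AEs are still documented.** They go on the forms, are reviewed by a physician, and are reported to the sponsor within 24 hours if severe. This stands: the events do not vanish from the records. It does not put them back in the rate.

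**Analysis Overview says missing values are not imputed.** That supports leaving unknown outcomes unknown. It does not support dropping observed ones, and the default moderate AE is itself an imputation.

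**The call rule may be a specific exception to a general one.** That is plausible, and the overlap is narrow, but neither section refers to the other.

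**A client seen at an unscheduled visit or reported by another health centre may not count as lost.** This is arguable. The clean case is a placement AE followed by non-return.

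**The numbers rest on assumptions, some of them severe.** This is correct. Three recorded AEs among 29 lost is 10.3%, about five times the planning rate; at 2% one would expect 29 × 0.02 = 0.6. The all-AE bound is an extreme. The evidence on informative loss is mixed too: Appendix XIX grades self-removal and displacement as moderate or severe AEs, but the delayed-removal study the protocol cites reported no severe or serious events.

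**Conclusion.** The concern holds. As written, the rule excludes observed AEs that the primary endpoint is defined to count, and it contradicts the default-AE rule for callers lost before removal, with no stated precedence. The protocol itself fixes the rule, so this is not detail left to an analysis plan.

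The scope is limited. Only clients who remain untraced after active follow-up are affected, and the number failing to return will be reported, although that count neither restores their AEs nor shows how far the rate depends on them. Neither the size nor the direction of bias is established. If no lost client had an AE, the rule slightly raises the rate (1.95% against 1.91% with 12 lost). It understates the rate when AEs are more frequent among the lost than among those who return. With roughly 11 events expected, a handful of clients can move the result noticeably. This should be corrected before analysis.

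**What to change.** 1. Amend the loss-to-follow-up section so that every client with a device placed stays in the AE analysis and every AE known up to last contact is counted. The statement that loss alone is not scored as an AE can remain.
2. Reconcile that section with Client Withdrawal Criteria and the section on client-initiated calls. State one analysis rule for untraced clients with an open AE complaint, and cross-refer.
3. Beside the AE rate, report the number lost before removal and the rate with none and with all of the lost counted as AEs. This must accompany the first change, because an all-placed denominator on its own treats unknown outcomes as no AE (11/575 = 1.91% against 11/546 = 2.01% with 29 lost).
4. Add a line in Analysis Overview that the default AE and the bounds are stated exceptions to the no-imputation rule.

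The cost is one amended paragraph, a cross-reference, one sentence and one small table. No further data are collected and client management does not change. The reported rate may shift slightly in either direction.
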